## 7. Analysis Populations

Efficacy analyses will be generated for the ITT and Per Protocol (PP) Population. Safety data will be reported on all enrolled subjects who undergo a procedure from implantation of the study device. Figure 1, below shows the patient disposition schema for each of the analysis populations.

Figure 1 Analysis Populations

## 7.1. Per Protocol Population

The Per Protocol population will include all subjects in the Intent to Treat population with no major protocol deviations. Subjects in the PP population must remain OAB drug-free for the duration of the study. Additionally, subjects should not have any significant departures from the amplitude programming. This is the primary and secondary endpoint analysis population.

## 7.2. Intent-to-Treat

All enrolled subjects who undergo a procedure for implantation of eCoin and are randomized to a treatment arm and who have data available at the baseline and primary endpoint.

## 7.3. Safety Population

All enrolled subjects that undergo a procedure for implantation of eCoin. This will be the primary analysis population for the safety analysis.

## 8. General Statistical Conventions and Considerations

Descriptive statistics will summarize results of the ESSENCE protocol. Standard descriptive statistics, such as number of subjects, mean, standard deviation, quartiles, minimum, and maximum, will be calculated for continuous variables. For discrete variables, summary tables will display numbers of subjects and related percentages. Tables will display three columns of results showing all data as well as the sensory and subsensory treatment arms. The general statistical conventions and definitions used for the data analysis are described below.

### 8.1. Key Definitions

#### 8.1.1. Baseline

Baseline efficacy measures will be defined as the last measure taken up to and including the baseline visit (Visit 2). Baseline safety measures will be defined as the last measure taken prior to device implantation.

## 8.1.2. Diary Data

### 8.1.2.1. UUI Episodes

A UUI episode is defined as a leak that is not being caused by physical movement as indicated on the voiding diary.

### 8.1.2.2. Total Leakage

Total leakage is defined as any leak (stress or urge) as indicated on the voiding diary.

### 8.1.2.3. Amount of Accidental Urine Leakage

Amount of accidental urine leakage is defined as the total leakage volume categorized as small, medium, and large leaks and calculated in the Database using the calculation:

$$1 \text{ X Small leak} + 2 \text{ X Medium Leak} + 3 \text{ X Large Leaks.}$$

## 8.1.3. Diary Completion

A voiding diary is considered complete if the CRF question “Did the subject adequately complete the 72-hour diary” is answered “yes.” Diaries may be redone, reconciled, and averaged as described in section 8.6.3 Missing or Incomplete Diary.

## 8.1.4. Study Exit

A subject’s study exit date will be defined as the study exit date on the study exit CRF.

## 8.1.5. Study Completion

A subject will be defined as “completed” if he/she completes the 4-month post-activation study visit.

## 8.2. Derived variables

### 8.2.1. Age

Age in years will be calculated as the integer portion of the following:

$$[(\text{Date of enrollment} - \text{Date of birth}) + 1] / 365.25$$

### 8.2.2. BMI

BMI will be calculated using the following equation:

$$703 \times [(\text{Weight in pounds}) / (\text{Height in inches}^2)]$$

### 8.2.3. Study Days

For the analysis, study day will be calculated relative to device implantation or initial activation, depending on the analysis:

- Study day relative to implantation = date of visit/test – implantation date + 1.
- Study day relative to activation = date of visit/test – activation date + 1.

If the date of a visit or test occurs before the date of interest, then study day = date of visit (or test) – implantation/activation date. The study does not define a Day 0.

### 8.2.4. UUI Episodes per Day

UUI episodes per day will be calculated as an average over 3 days.

$$\text{UUI episodes per day} = (\text{UUI Day 1} + \text{UUI Day 2} + \text{UUI Day 3}) / 3$$

### 8.2.5. Change from Baseline

Change from baseline will be calculated for the key primary and secondary endpoints for both UUI data and HRQL data.

Change from baseline will be calculated as follows:

$$\text{CFB} = \text{Post-baseline UUI Episodes per day} - \text{UUI Episodes per day at baseline}$$

For HRQL data, change from baseline will be calculated using the composite score as follows:

$$\text{CFB: Post-baseline composite score} - \text{Baseline composite score}$$

## 8.3. Timing of Analysis

### 8.3.1. Interim Analysis

No interim analysis is planned for this study.

### 8.3.2. Primary Endpoint Analysis

The primary analysis will be performed after all subjects complete 3 months of therapy. The analysis will be performed on a locked Excel database that has been documented as meeting the cleaning and approval requirements of the DMP. Analysis will occur only after this SAP has been approved and a database lock form has been completed. The primary analysis may include but is not limited to:

- Study population summaries
- Primary efficacy outcome
- Secondary efficacy outcome through 3 months post-activation

### 8.3.3. End of Study Analysis

A final analysis will be performed after all subjects complete 4 months of therapy and are exited from the study. The analysis will be performed on a locked Excel database that has been documented as meeting the cleaning and approval requirements of the DMP. Analysis will occur only after this SAP has been approved and the second database lock has been documented. The secondary analysis may include but is not limited to:

- Study population summaries
- Secondary efficacy outcome after 4 months of therapy
- Sensitivity and additional analysis
- Exploratory subgroup analysis

## 8.4. Changes to Planned Analysis

Changes to the analyses described in this plan will be fully documented in a revised version of the plan written prior to locking the study database and conducting the primary outcome analysis. Changes should be documented and approved before

unblinding occurs. Changes made after locking the study database will be described in the clinical study report and characterized as “exploratory”.

## 8.5. Center Pooling

The ESSENCE study is a multi-center study and data from all study centers will be pooled for analysis. There are no planned statistical methods to test for treatment-by-center interactions.

## 8.6. Missing Data

### 8.6.1. Premature discontinuation from the study

Any subject that does not have follow-up data at the timepoint being analyzed will be excluded from the dataset.

### 8.6.2. Incomplete Dates

Completely missing dates will not be imputed.

Partial dates in the medication and adverse events data will be imputed. Partial start dates will be imputed as follows:

- Dates with only missing day will be imputed to the first of the month; however, if the month and year of the partial date are the same as the month and year of the device implantation date, the partial start date will be imputed to the device implantation date.
- Dates with missing day and month will be imputed to January 1st of the given year; however, if the year of the partial date is the same as the year of the device implantation date, the partial start date will be imputed to the device implantation date.

Partial end dates will be imputed as follows:

- Dates with only missing day will be imputed to the end of the month.
- Dates with missing day and month will be imputed to December 31st of the given year.

### 8.6.3. Missing or Incomplete Diary

All reasonable efforts will be made to ensure that all diaries are completed over the full three-day period. Any incomplete diaries with data available for 2 out of 3 days will be reported and averaged over the total days in which they were completed.

In some cases, patients may be required to redo their diary. Examples of these scenarios are described below:

- It is missing more than 1 day of data entry
- It is filled out incorrectly and unable to be reconciled
- It is illegible and unable to be reconciled
- It is considered incomplete at the discretion of the site staff

In these scenarios, the revised diary data and associated dates will prevail over the original and will be included in the analysis.

If a subject is unwilling or unable to complete or reconcile and incomplete diary, their data will be excluded from the analysis.

A CRF field will exist on the baseline and follow-up CRFs asking whether the diary is complete. If a diary is redone or reconciled, this box should be changed from “no” to “yes.” If the diary is missing or irreconcilable, this box should be checked “no.” Reconciliation efforts and/or diary redo scenarios should be documented in protocol deviation forms.

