The COVID-19 pandemic may prevent subjects from coming into the clinical site for follow up visits. As an alternative, subjects may complete remote visits, in which all study activities can be performed. Patients will electronically transmit their diary and OABq/satisfaction survey responses to the site personnel, through either pictures, scans, or fax, and review all other items over the phone. If subjects or site personnel send diaries through the mail, tracked delivery services should be used. Changes in study visit schedules, remote visits, missed visits, or patient discontinuations due to COVID-19 will be documented and will be included in the final study visit report.

2-4-1 Recruitment Plans

Investigators will identify patients under their direct care and contact patients who appear to qualify from medical records. Investigators will also seek referrals from other urology, urogynecology, gynecology and primary care practices. Patients with a medical history of urgency urinary incontinence and who appear to meet the inclusion and exclusion criteria will be presented with the opportunity to participate in the study.

Such discussions may be informal or formal, may occur after a patient is scheduled for implantation of the eCoin System, or may occur alongside a discussion between the physician and patient about the patient's treatment options.

Patients who remain interested will be brought into the research clinic for further screening and informed consent.

The study device will be provided free of cost by Valencia Technologies.

2-4-2 Visit Overview

The enrollment process consists of screening (including obtaining written consent) and completing the baseline evaluation. After confirming eligibility, the eCoin system will be implanted, the subject will be randomized and the amplitude will be set depending on their randomization group. A revision procedure would not reset the initial activation date.

After all assessments for the 3 month visit have occurred (questionnaires, etc), the patient and physician will be unblinded by the Field Clinical Engineer (FCE) attending the visit. The FCE will then offer the subject reprogramming and provide the subject with information on the expected battery life and depletion date. This information allows for adequate time to prepare for and schedule eCoin device explant or replacement.

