For the visit involving a 3-day diary, the diary should be completed over 3 consecutive days during the 7 days prior to the indicated visit

- Visit 1: Screening Procedures (informed consent, demographic and medical history and concomitant medication/therapy information, physical examination, and vital signs are collected, subjects begin 2 week wash-off of OAB medications or 4 week wash-off of PTNS if applicable, eligibility determination)
- Visit 2: Baseline Assessments (3-day voiding diary, OABq, patient satisfaction survey, concomitant therapy review, final eligibility determination) (Time: Between 3 and 32 days from Visit 1)
- Visit 3: Implant Procedure (vital signs collected, adverse event assessment, concomitant therapy review, pictures taken) (Time: Between 0 and 20 days from Visit 2)
- Visit 4: Incision Healing Check (vital signs collected, adverse event assessment, pictures taken, concomitant therapy review) (Time: Between 9 and 19 days from Visit 3)
- Visit 5: Initial Activation and Randomization at Sensory or Subsensory (vitals signs collected, adverse event assessment, pictures taken, concomitant therapy review) (Field Clinical Engineer present) (Time: Between 23 and 43 days from Visit 3)
- Visit 6 (2 months post-activation): Follow-up assessments (3-day voiding diary, OABq, patient satisfaction survey, adverse event assessments, concomitant medication therapy review) (Time: Between 7 and 9 weeks from Visit 5)
- Visit 7 (3 months post-activation): Follow-up assessments (3-day voiding diary, OABq, patient satisfaction survey, adverse event assessments, concomitant medication therapy review, unblinding and reprogramming as requested (Field Clinical Engineer present)) (Time: Between 12 and 14 weeks from Visit 5)
- Visit 8 (4 months post-activation): Follow-up assessments (3-day voiding diary, OABq, end of study survey, adverse event assessments, concomitant medication therapy review) (Time: Between 16 and 18 weeks from Visit 5)

	Screening	Baseline	Implantation	Incision Healing Check	Activation (Follow up Clock Starts)	2 Month	3 Month: Primary Endpoint	4 Month
Demographics, screening exam, physical exam, & medical history	X							
Eligibility Determination	X	X						
Informed Consent	X							
3-day Voiding Diary Reminder Call		X				X	X	X
3-day Voiding Diary		X				X	X	X
OABq Assessment		X				X	X	X
Patient Satisfaction Survey		X				X	X	
End of Study Survey								X
Implant Procedure			X					
Incision Assessment				X				
Pictures Taken			X	X	X			

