All subjects will return for a device activation visit approximately four weeks after implantation. At this point, the follow-up visit clock will start to run (that is, the follow-up visits will be characterized in relationship to the date of the activation visit).

The subject will be provided with a 3-day voiding diary to complete in the 7 days prior to the next visits (occurring 2 and 3 months post-activation). At least 3 days prior to the next visit, a member of the study staff will telephone subjects to remind them that they should begin the 3-day diary.

2-4-10 Establishment of the Amplitude Setting in each Treatment Arm

Amplitude level ranges in practice from 0.5 to 15 mA. Sensory threshold is defined as the lowest amplitude where the subject first perceives sensation of the stimulation in the foot, heel, toes or eCoin device site while in a prone, seated and standing position.

Subjects will be informed that they may periodically feel a tingling or notice a muscle twitch. In particular, subjects may feel a motor response (flexing of the big toe and/or fanning of the other toes) and sensory response (a radiating sensation may be felt at the sole of the foot and in the toes). Typical descriptions of tibial nerve stimulation sensation include feeling a 'buzzing', 'tingling' and 'vibrating' sensation.

2-4-10-1 Sensory Treatment Arm Activation Protocol

The subject's sensory threshold is determined by turning the device on to 0.5 mA and increasing the amplitude by one level until the subject reports sensation. If the subject does not feel sensation at any amplitude, they will be set at 8 mA, this will be considered a deviation to the protocol.

2-4-10-2 Subsensory Treatment Arm Activation Protocol

The subject's sensory threshold is determined by turning the device on to 0.5 mA and increasing the amplitude by one level until the subject first reports sensation. Once the first sensory threshold is determined, the set amplitude will be lowered to approximately 75% of the sensory threshold, accounting for rounding. Patients who do not have sensory at the highest amplitude will be set at 11mA. See the below table for sensory threshold and level set correlations:

Sensory Threshold	Level Set
0.5 mA	Protocol Deviation, set 0.5 mA
1 mA	0.5 mA
2 mA	1 mA
3 mA	2 mA
4 mA	3 mA
5 mA	4 mA
6 mA	5 mA
7 mA	5 mA
8 mA	6 mA
9 mA	7 mA
10 mA	8 mA
11 mA	8 mA
12 mA	9 mA
13 mA	10 mA
14 mA	11 mA
15 mA	11 mA
No sensation	11 mA

2-4-11 Post Activation Follow-up Procedure

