- 2) Any non-emergency, major deviation to the protocol must be approved by the Sponsor prior to implementation. If a major deviation occurs that is not in response to the protection of a subject, falls into the above categories or was not pre-approved by the sponsor, it must be reported to the Sponsor and IRB as non-compliance – no later than 5 days after the deviation. A PI's failure to report promptly any major deviation will be evaluated by the Sponsor. Such failure could be grounds for physician disqualification.

2-7-6-2 Minor or Administrative Protocol Deviations

A minor deviation is defined as one that does not affect the safety of the subject or the scientific validity of the results. Minor deviations from the protocol should be noted through the protocol deviation CRF and brought to the attention of the monitor at the next monitoring visit. These deviations do not need to be reported to the IRB/Ethics Committee.

Examples of a minor protocol deviation follow:

1. Deviations related to amplitude programming or use of the patient controller. For example:

111-6133	Clinical Study Protocol ESSENCE	Rev: 1	Date Printed:4/10/2025	Page 33 of 38
----------	---------------------------------	--------	------------------------	---------------

- a. Unable to feel sensation at any level for sensory arm,
- b. Sensory threshold is at lowest setting for subsensory arm
- c. Reprogramming that is a departure from the assigned treatment stimulation
- d. Device not activated
- e. Device turned off prior to primary endpoint

- 2. Follow-up visits that occurred outside the protocol required time frame because of the participant's schedule.
- 3. Study procedure conducted out of timeframe, e.g., 3-day diary
- 4. Participant failure to return patient diary
- 5. Copy of the ICF not given to the participant
- 6. Missing original signed consent, but a copy exists

Missed vitals at a follow-up visit is not considered a protocol deviation.

2-7-6-3 Analyzing Deviations

At each monitoring visit, the deviations will be reviewed along with any additional deviations that might be discovered during the monitoring visit. If any minor deviation is deemed to have an impact on the trial outcomes, the issue must be brought to the attention of the Sponsor.

2-7-7 Modification of the Protocol

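### Nothing in the plan stops a 3-month diary redone after the Visit 7 unblinding, and possibly after reprogramming, from becoming the primary endpoint value

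*SAP*

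**What the plan says.** **Diary timing.** For visits with a diary, Protocol 2-4-2 states that "the diary should be completed over 3 consecutive days during the 7 days prior to the indicated visit". Subjects bring the diary to the visit (Protocol 2-4-11). The site's study coordinator reviews it (Protocol 2-4-13), but no time is given for that review. SAP 8.1.3 counts a diary as complete once the adequacy question on the CRF is answered yes.

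**Unblinding.** Protocol 2-4-2 states: "After all assessments for the 3 month visit have occurred (questionnaires, etc), the patient and physician will be unblinded". The Field Clinical Engineer (FCE) does this and then offers reprogramming. SAP 5.4 also places unblinding at the end of the 3-month visit. The visit window is 12 to 14 weeks after activation.

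**Redo.** SAP 8.6.3 gives four examples of when a diary may have to be redone: more than one day missing, incorrect entries that cannot be reconciled, illegibility that cannot be reconciled, and an open-ended one, "It is considered incomplete at the discretion of the site staff". For all of them, "In these scenarios, the revised diary data and associated dates will prevail over the original and will be included in the analysis". The CRF box is then changed from no to yes, and the redo is documented on a deviation form. A diary lacking a single day has its own rule: "Any incomplete diaries with data available for 2 out of 3 days will be reported and averaged over the total days in which they were" [filled in].

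**Analysis sets.** Protocol 2-7-6-2 lists as an example of a minor deviation: "Study procedure conducted out of timeframe, e.g., 3-day diary". SAP 7.1 removes major deviations and significant programming departures from the per-protocol set. SAP 9.6 words the reprogramming departure as one occurring before 3 months. SAP 10.4.2 defines the blinded subgroup by whether the blind held through 3 months post-activation.

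**The concern.** The primary endpoint is a self-reported count, and blinding is what protects it. The redo rule replaces a diary kept under the blind with a later one and does not ask whether the blind still held when the later one was kept. For such a subject the 3-month value would be reported with the arm known. If reprogramming was accepted, it would also be reported at an amplitude other than the assigned one, and so would measure neither a blinded outcome nor the randomised setting.

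The arm means and their 95% confidence intervals are the primary result, and contrasting the two settings is the purpose of the study. Reprogramming is optional and may be taken up unevenly, so the distortion need not cancel between arms. If adequacy is judged after unblinding, the open-ended site-discretion trigger would also be applied by staff who know the arm.

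**Working it through.** **1. Order of events for a diary rejected at Visit 7.**
- The diary is kept in the 7 days before the visit and handed in at the visit.
- A redo needs three more consecutive days, so it ends after the day of the visit.
- The protocol synopsis (Follow-up, 3 Month), Protocol 2-4-2 and SAP 5.4 put unblinding at the end of that visit.
- The redo therefore falls after unblinding unless unblinding is deferred. Neither document describes a deferral.
- SAP 8.6.3 then directs the analyst to the redone diary and its dates.

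**2. Would another rule remove it?**
- Deviation class: a diary outside its timeframe is an example of a minor deviation (Protocol 2-7-6-2), and only major ones lead to exclusion (SAP 7.1). This does not clearly remove it.
- Reprogramming: SAP 9.6 covers reprogramming before 3 months. Visit 7 reprogramming is planned, so it is not a departure. Protocol 2-6-4-2 omits the time limit, but read literally it could also remove subjects whose valid 3-month diary preceded a planned Visit 7 reprogramming, which can hardly be intended.
- Blinded subgroup: it depends on the blind through 3 months, not on diary dates. A subject unblinded on schedule at Visit 7 can qualify with a diary kept afterwards.
- Missing data: SAP 10.3 plans no sensitivity analysis.

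**3. The plan's precision figures, reproduced.** Inputs from SAP 6: SD 2, two-sided 0.05, D = t(0.975, n−1) × SD / √n.
- n = 16: 2.131 × 2 / 4 = 1.07. Around the assumed reduction of 1.3 this gives (0.23, 2.37), as stated.
- n = 13: 2.179 × 2 / 3.606 = 1.21, as stated.
- All eight tabulated values, n = 13 to 20, agree to two decimals.

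**4. Possible size.** If k diaries in an arm of n each shift by δ UUI episodes per day, the arm mean moves by k × δ / n. Neither k nor δ is in the documents. The range assumed is δ = 0.5, 1 or 2.

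| n | k | δ = 0.5 | δ = 1 | δ = 2 | half-width |
|---|---|---|---|---|---|
| 16 | 1 | 0.03 | 0.06 | 0.13 | 1.07 |
| 16 | 3 | 0.09 | 0.19 | 0.38 | 1.07 |
| 13 | 1 | 0.04 | 0.08 | 0.15 | 1.21 |
| 13 | 3 | 0.12 | 0.23 | 0.46 | 1.21 |

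The table spans about 3% (0.03/1.07) to 38% (0.46/1.21) of the half-width. With k = 0 the effect is zero.

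**5. Precision lost if such diaries are left out and no usable original exists.**
- From n = 16: 1.11 with one lost, 1.15 with two, 1.21 with three.
- From n = 13: one lost gives 2.201 × 2 / √12 = 1.27, still below 1.3. Two lost give 2.228 × 2 / √11 = 1.34, above 1.3.

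**The case against.** The strongest reply is that the protocol already orders the events correctly. Unblinding follows all 3-month assessments, and the visit list in 2-4-2 names the diary among them with unblinding last. Protocol 2-4-8 and SAP 5.3 keep the blind until the primary endpoint visit is complete. Since the diary is the primary endpoint, an unusable diary could mean that the visit is not complete, and the 12 to 14 week window can leave room to wait. This reading is fair, and it rules out the claim that the plan schedules redos after unblinding. It does not close the gap. A diary that was returned and then rejected can equally be taken as an assessment that has occurred, and SAP 8.6.3 contains no condition either way.

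A reader might infer that such a subject automatically stays in the per-protocol set. The documents do not support that. A deviation that affects scientific validity is major (Protocol 2-7-6-1, SAP 9.5), redos go on deviation forms, and Protocol 2-7-6-3 sends minor deviations with an impact on outcomes to the sponsor. Exclusion is possible, but it is left to case-by-case judgement.

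Exposure is also limited. A diary with two usable days is averaged and needs no redo on that ground, incorrect or illegible diaries are reconciled first where possible, and reprogramming is optional. The ESSENCE Blinding Work Procedure cited in SAP 5.3 was not available and may order these steps. Even so, the SAP's analysis rule would need its own date limit.

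A reader might extend the point to the baseline diary or to the reminder call. Neither adds much. Final eligibility depends on review of the baseline diary and precedes implantation, which largely covers the first. The call timing is a stated minimum, and nothing in the documents links it to inadequate diaries.

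**Conclusion.** The point holds as a gap: the plan does not prevent unblinded, possibly reprogrammed, diary days from becoming a subject's 3-month primary value, and no other rule clearly removes them. It does not show that this will happen, or that the plan intends it.

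The size rests on two unknowns, the number of redone 3-month diaries and the shift in each. Under the assumed shifts, a single diary moves an arm mean by at most 0.15 UUI episodes per day at n = 13, about 13% of the half-width (0.15/1.21). Three in the same arm could move it by up to 0.46. The upper shift of 2 is generous, since it equals the planning SD and is close to the 8-week mean reduction of 2.3 given in SAP 6.

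A reader might infer that the gap invalidates the primary analysis. It does not. The endpoint is exploratory, with no success criterion and no powered comparison (SAP 10.1), so no power or alpha figure changes. What is at stake is bias in the arm means and in their contrast. Severity is moderate, and the correction is cheap.

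**What to change.** 1. **SAP 8.6.3.** Add that a redone 3-month diary with any day on or after that subject's unblinding or reprogramming does not replace the original and does not enter the primary endpoint or the blinded-subgroup analysis (SAP 10.4.2). Use the original diary if at least two of its three days are usable; otherwise treat the value as missing. Keep both diaries with their dates, and report the number of such cases by arm.
2. **Protocol 2-4-2, Visit 7.** State that the diary-adequacy question is answered before the planned unblinding. Reconcile Protocol 2-4-2, SAP 5.4 and SAP 8.6.3 on what happens when the answer is no.

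Both should be in place before database lock, because SAP 8.4 labels later changes exploratory.

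The cost is wording plus an occasional missing 3-month value. Starting from 13 per arm, the half-width rises from 1.21 to 1.27 with one lost and to 1.34 with two, the latter above the plan's 1.3. If the sponsor resolves item 2 by having unblinding wait, the FCE would have to attend a second time for those subjects.
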